2.5 Pain assessment and the numeric pain rating scale (NPRS)

In the conventional radiation setting, the International Consensus Pain Response Endpoints (ICPRE) has been developed for clinical endpoints as pain for bone metastases²¹. In this protocol, we will use the ICPRE to evaluate pain response. Response categories are based on patient reported pain scores (NPRS) and analgesic consumption (convert to oral morphine-equivalent dose).

NPRS ranges from '0' representing one pain extreme (e.g. "no pain") to '10' representing the other pain extreme (e.g. "pain as bad as you can imagine" or "worst pain imaginable"). See Appendix C.

Registration of NPRS will be registered at baseline and subsequently according to Table 2. Analysis of pain reduction will only include patients with $\text{NPRS} \geq 1$ registered at baseline. We intend to report the best response during follow-up. If more than one lesion is treated, the index lesion will be used to assess the pain response. The index lesion is defined as the lesion with the highest pretreatment pain score. If a patient has two or more lesions with the same maximum pain score, the index lesion is defined as the most cranial located lesion.

- A complete pain response is defined as a pain score of 0 out of 10 at the treated site with no concomitant increase in analgesic intake
- A partial pain response is defined as a pain reduction of 2 or more at the treated site without analgesic increase, or an analgesic reduction of 25% with no increase in pain score or 1 point above baseline.
- Pain progression is defined as an increase in pain score of 2 or more above baseline with stable analgesic intake or an analgesic increase of 25% with stable pain score.
- An indeterminate response is any response not captured in the above definitions.

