For each of the first five weeks, where daily measurements are recorded, the peak value will be used for analysis. Changes in severity score over time (repeated measurement) will be analyzed using Generalized Linear Mixed Models.

C. Duration of dysphagia, nausea and dyspepsia measured by NCI-PRO-CTC-AE [Time Frame: within five weeks after start of RT (daily measurements) and at 6, 7, 8, and 9 weeks].

Duration of toxicity will be presented graphically in separate figures.

For the first five weeks mean duration (days) in each group will be compared using Wilcoxon rank-sum test.

D. Severity of cough, oropharyngeal pain, dyspnea, dysphagia, hoarseness, and dyspepsia measured by CTC-AE (weekly measurements) [Time Frame: Week 1-5 after start of radiotherapy (repeated measurement)].

CTC-AE responses are scored from 0 to 4, with 0 representing “None” and 4 representing “Very severe”.

Changes in severity score over time (repeated measurement) will be analyzed using Generalized Linear Mixed Models.

E. Duration of cough, oropharyngeal pain, dyspnea, dysphagia, hoarseness, and dyspepsia measured by CTC-AE (weekly measurements) [Time Frame: Week 1-5 after start of radiotherapy (repeated measurement)].

Duration of toxicity will be presented graphically in separate figures. Mean duration (weeks) in each group will be compared using Wilcoxon rank-sum test.

F. Demographics: Subject demographics, baseline characteristics and medical history will be summarized descriptively. Generally, range, mean and standard deviation, or median and inter quartile range, will be reported for continuous variables. Frequencies and proportions will be reported for categorical variables.

G. Treatment site pain response [Time frame: weekly, 1-9 weeks after start of RT]:

Only patients with baseline pain will be included in the analysis.

Pain response will be measured by the ICPRE score (6). Possible responses are “Complete response”, “Partial response”, “Pain Progression” and “Intermediate response”.

For each of the first five weeks, where daily measurements are recorded, the worst response will be used for analysis. Changes in ICPRE score over time (repeated measurement) will be analyzed using Generalized Linear Mixed Models.

H. Duration of treatment site pain response [Time Frame: Weekly week 1-9 after start of radiotherapy].

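### Read literally, the pain-progression rule files a patient whose pain and analgesics both rise as indeterminate, while a patient who worsens on only one of them is progression

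*Protocol*

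**What the plan says.** Protocol section 2.5 adopts a consensus instrument ("In this protocol, we will use the ICPRE to evaluate pain response") and then spells out four categories from the NPRS score and analgesic use.

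- Complete response: "a pain score of 0 out of 10 at the treated site with no concomitant increase in analgesic intake".
- Partial response: "a pain reduction of 2 or more at the treated site without analgesic increase, or an analgesic reduction of 25" per cent, the second alternative holding only if pain has not risen by more than 1 point.
- Pain progression: "increase in pain score of 2 or more above baseline with stable analgesic intake or an analgesic increase of 25% with stable pain score".
- Remainder: "An indeterminate response is any response not captured in the above definitions".

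Section 2.5 gives no numerical meaning for *stable*, and no sentence covers both components rising.

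The SAP restates none of these rules. Item G classifies by citing the consensus and lists four labels, the last printed as an intermediate response. For each of weeks 1 to 5, items G and H say that "the worst response will be used for analysis". Item G fits generalized linear mixed models, and the analysis summary table gives the data type as ordinal, repeated measurement. No order of the four categories is stated. The protocol's own summary measure differs: "We intend to report the best response during follow-up".

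**The concern.** Each limb of the progression rule requires the other component to be stable, so the limbs cover worsening on one component but not on both. Analgesics are prescribed at the referring physician's discretion (Protocol section 4.4), so a rise in pain can be met with a rise in analgesics. Patients with both changes are therefore to be expected, and the written rule takes them out of the progression category.

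This matters because the experimental plan may give up target dose to spare the esophagus (Protocol section 6.4), and whether that costs efficacy is a stated objective (section 9.1). Pain response is a secondary endpoint and also enters SAP item O, which relates it to target coverage. A scale on which a patient can move out of progression by getting worse on a second component is a weak instrument for that question.

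**Working it through.** No figure in the documents depends on this rule, so there is none to reproduce. The check has three parts.

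**1. Classifying patients by the written rule.** Inputs are the four definitions in section 2.5 and three possible readings of *stable*: (a) unchanged; (b) below the protocol's own thresholds, meaning pain within 1 point and analgesics changed by less than 25%; (c) not decreased. For a patient with baseline NPRS 5:

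| Follow-up pain | Analgesic change | (a) | (b) | (c) |
|---|---|---|---|---|
| 5 | 0% | Indeterminate | Indeterminate | Indeterminate |
| 7 | 0% | Progression | Progression | Progression |
| 5 | +25% | Progression | Progression | Progression |
| 7 | +10% | Indeterminate | Progression | Progression |
| 6 | +25% | Indeterminate | Progression | Progression |
| 7 | +25% | Indeterminate | Indeterminate | Progression |
| 9 | +100% | Indeterminate | Indeterminate | Progression |

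Over the whole scale, baseline scores 1 to 8 with a rise of at least 2 give 8+7+6+5+4+3+2+1 = 36 pairs. Crossed with analgesic rises of 25%, 50% and 100%, that is 36 × 3 = 108 combinations. Under (a) and (b), 108 of 108 are indeterminate. Under (c), 108 of 108 are progression.

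Readings (a) and (b) are the ordinary ones: 2 points and 25% are the protocol's own thresholds for change, so a component that has crossed its threshold is hard to call stable. The text does not state reading (c).

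**2. Consequence for an ordinal analysis.** The first and last rows of the table share a category under (a) and (b): an unchanged patient and one whose pain is 4 points higher on doubled analgesics.

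- If indeterminate ranks better than progression, the patient at pain 9 with +100% scores better than the patient at pain 7 with 0%.
- If it ranks worse than progression, the unchanged patient scores worse than one who has progressed.

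Neither position works, so stating the order does not by itself repair the rule. The SAP's weekly worst-response step depends on the same unstated order.

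**3. How many patients could be affected.** The documents give no distribution of pain or analgesic change, so every input here is an assumption: NPRS change with mean −1 and SD 2.5; log analgesic change with mean 0 and SD 0.5; correlation 0 to 0.7. Misfiled share = both-up ÷ (both-up + worsening on one component only).

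- Low end (correlation 0, unrounded pain change, any fall in the other component allowed as stable). P(pain ≥ +2) = P(Z ≥ 3/2.5 = 1.2) = 0.115. P(analgesics ≥ +25%) = P(Z ≥ ln 1.25/0.5 = 0.446) = 0.328. Both: 0.115 × 0.328 = 0.038. Either: 0.115 + 0.328 − 0.038 = 0.405. Share: 0.038/0.405 ≈ 9%.
- High end (correlation 0.7, whole-point pain change, reading (b); simulation of 2,000,000 draws). Both-up 12.5%, one component only 19.8%. Share: 12.5/(12.5 + 19.8) ≈ 39%.

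The model ignores the 0 to 10 limits of the scale and puts no mass on unchanged analgesics, so the range is only illustrative.

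**The case against.** The strongest reply is that *stable* is undefined and the SAP classifies by citing a consensus that may settle the case. An analyst who took the word to mean not decreased would code all these patients as progression. That stands as a limit on certainty: the defect depends on the ordinary reading. It does not remove the point, because neither document states the favourable reading, and the cited source cannot be checked here and is not relied on.

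A second reply is that the consequence is narrow. This is right. A both-up patient cannot be a complete responder, because analgesics have risen, nor a partial responder, because pain has not fallen and analgesics have not been reduced. Responder classification is therefore unchanged, and item H is largely untouched if its duration refers to complete or partial response.

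A reader might infer three stronger things, which the documents do not support.

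- *The rule shrinks a between-arm difference in progression.* One can build such a case. With the assumptions above, correlation 0.5 and an experimental arm shifted to mean NPRS change 0 and mean log analgesic change 0.2, written progression is 21.7% against 29.0% (7.3 points), while progression including both-up patients is 31.8% against 49.1% (17.3 points). That result comes from assuming an arm that is worse on both components. The SAP also plans no between-arm comparison of progression rates; it plans an ordinal mixed model.
- *The misfiled patients are the clearest local treatment failures.* The documents speak of pain progression, not failure, and Protocol section 9.2.2 describes temporary worsening of pain at the treated site.
- *The trial loses its check on efficacy.* Mobility (co-primary), re-irradiation, and the pain items of EQ-5D-5L and QLQ-C30 remain. The protocol also lists NPRS reduction and analgesic change as separate secondary endpoints, although the SAP sets out no separate analgesic analysis.

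**Conclusion.** The point holds as a defect in a classification rule. On the ordinary meaning of *stable*, all 108 both-up combinations examined are indeterminate while milder one-component worsening is progression, and nothing in the SAP repairs this. It affects one category of one secondary endpoint and the analyses built on it (SAP item G, and item O where it uses pain response). It does not affect either co-primary endpoint, the sample size, or complete and partial response. The share of worsening patients misfiled is about 9% to 39% under assumed distributions, and the documents give no basis for narrowing that range. Whether either arm would benefit, and by how much, cannot be computed. The change is worth making before analysis because the rule runs the wrong way, not because a bias of known size has been shown.

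**What to change.** In Protocol section 2.5 and SAP items G and H:

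1. Add a third limb: a pain rise of 2 or more together with an analgesic rise of 25% or more is pain progression. All 108 combinations then become progression.
2. Define *stable* numerically, for example pain within 1 point of baseline and analgesic dose changed by less than 25%. One edge case needs a decision under that example: baseline pain 1, follow-up 0 and analgesics up 25% would count as progression.
3. State the order of the four categories used for the weekly worst response and in the ordinal mixed model, and use one name for the residual category in both documents.

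A wider rewrite of the progression definition is not needed, as it would also move other combinations.

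The cost is a few sentences and recoding of NPRS and analgesic data that Protocol Table 2 already schedules. The downside is a small departure from the definition as written, so tabulate the as-written category alongside as a sensitivity analysis.

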2.6 HbA_{1c} validation

Baseline HbA_{1c} is measured for all patients starting high glucocorticoid treatment for MSCC. Baseline values above 48 mol/mol are considered diagnostic for DM. For all other patients, diabetes developed during glucocorticoid treatment will be defined as two random plasma glucose measurements ≥ 11 mmol/L. Based on baseline HbA_{1c} results and subsequent glucose measurements from the patients included in ESO-SPARE we will validate if the current HbA_{1c} cut off value (39 mmol/mol) can identify patients in low risk of developing glucocorticoid-induced insulin-dependent DM.

2.7 Exploratory studies

- Description of the dose-response relationship for the esophagus in the palliative dose spectrum.
- Atomization strategies: from delineation of risk organs to dose calculation.
- Adaptive esophagus sparing strategies.

3 Study design, sample size calculation and time frame

3.1 Study design

This is a prospective, investigator-initiated, phase III, multicenter-study, investigating if esophagus sparing radiotherapy for spinal cord compression can decrease patient reported gastro-esophageal toxicity without compromising their ambulatory function.

Concurrently we want to validate the HbA_{1c} cut-off value used in the clinic to identify patients in low risk of developing glucocorticoid-induced insulin-dependent DM and characterize the spontaneous course of plasma glucose levels during and after treatment with high-dose glucocorticoids.

3.2 Sample size

Esophagus-sparring radiotherapy: 200 patients will be included in this study. Accrual and compliance will be assessed after inclusion of the first 50 patients. If compliance falls below 50% in more than 1/4 of patients, accrual will be extended to 250 patients. If compliance falls below 50% in more than ½ of patients, accrual will be extended to 300. Following study closure, 9 weeks of follow up after start of treatment is completed, before data are collected for primary end-point analysis. OS analysis will be performed 6 month, 12 and 18 months after the last patient has completed radiotherapy.

Glucocorticoid-induced diabetes: 150 patients will be included in this study. If needed, inclusion may continue after closure of inclusion for esophagus-sparring radiotherapy.

Analysis of data in respect to secondary endpoints and exploratory studies may be analyzed at any point of time, at the discretion of the study group. Data will be kept in databases 10 years after the last patient is included.

3.3 Sample size calculation for primary endpoint

We assume that we can decrease maximum esophageal dose from 30 Gy to 10 Gy and that this will result in a 50% decrease in risk of early esophageal toxicity.¹¹ We want to conduct a phase III trial with 1:1 randomization between standard VMAT and experimental esophageal VMAT. Prior data

indicate that the rate of early esophageal toxicity with standard VMAT is 0.6. ¹¹ If the true early esophageal toxicity rate in the esophagus sparing VMAT arm is 0.3, conventional power calculation indicates that we would need to include 62 patients in each arm, to be able to reject the null hypothesis that the toxicity rates for experimental and control arms are equal with a probability (power) of 0.9. The Type I error probability associated with the test of this null hypothesis is 0.05 and calculations are performed assuming Fisher's exact test. However, with this patient population we anticipate high rate of heterogeneity and we need to account for loss of follow-up due to patients dying early or being too frail. We increase the study size to 100 patients in each arm to account for these challenges. Patients will be stratified according to performance status and fractionation scheme.

3.4 Ambulatory function as a co-primary endpoint

We wish to demonstrate that the improvement in esophageal toxicity does not come at a price of reduced effect of the radiation. As a prioritized secondary endpoint, we choose ambulatory function (preserved ability to walk) measured on a 4-point scale. We assume that the conventional arm follows the distribution of the SCORAD trial and test our ability to detect a difference from an assumed inferior experimental arm in terms of ambulatory function, see Table 1.⁷

If the underlying “true” distribution on ambulatory grades is as depicted in the table and we assume 66 patients per arm are evaluable, we find that 84% of simulated trials would lead to statistically significant differences detected with a Wilcoxon rank sum test for comparing the trial arms. In other words, the power of the trial is enough to detect a deterioration according to the able, which would lead to rejection of the experimental treatment.

	Conventional arm	Experimental arm
Grade 1: Ambulatory without the use of walking aids	22	11
Grade 2: Ambulatory with walking aids	44	32
Grade 3: Unable to walk	26	37
Grade 4: Absence or flicker of motor power in any muscle group	8	20

Table 1: Distribution of ambulatory function. The conventional arm follows the SCORAD trial (7).

The power of ESO-SPARE is enough to detect a difference in ambulatory function as seen in Table 1.

3.5 Randomization

Patients will be randomized after signed informed consent. The randomization will be done in REDCap and be stratified for number of fractions and treating center. Patients will not be informed of randomization outcome. All patients can be included in validation of the HbA_{1c} cut-off after signed informed consent.

Patients from both arms can be included in validation of the HbA_{1c} cut-off after signed informed consent. Patients with prior history of diabetes and patients with HbA1c ≥ 48 mmol/mol will not be included. See **Figure 4** for patient distribution.

[figure not shown]

Figure 4. ESO-SPARE and GLUC-DIAB patient distribution.

3.6 Time frame

ESO-SPARE- Esophagus-sparring radiotherapy: 200 patients will be enrolled within a timeframe of maximum of three years. The study will close after three years regardless if the planned number of

enrolled patients is reached or not. Accrual and compliance will be assessed after inclusion of the first 50 patients. If compliance falls below 50% in more than 1/4 of patients, accrual will be extended to 250 patients. If compliance falls below 50% in more than ½ of patients, accrual will be extended to 300.

Compliance is defined as the patient's ability to answer at least half of the daily questionnaires within the first two weeks.

GLUC-DIAB - Glucocorticoid-diabetes: 150 patients will be enrolled within a timeframe of maximum of three years. The study will close after three years regardless if the planned number of enrolled patients is reached or not.

4 Visits and follow-up procedure

Patients will be scheduled for follow-up according to Table 2. Additional imaging or laboratory investigations are at the discretion of the treating oncologist. Inclusion of patients and recording of baseline data will take place when the patients come for the planning procedures for radiotherapy. Follow-up may be done electronically or using paper edition questionnaires. Paper edition questionnaires may be returned in relation to another hospital visit or by mail. Registration will be obtained from the patient's electronic records after they have signed informed consent. The clinical information registered will include age, sex, height, weight, smoking history, medical and surgical history, all medicine, performance status, pathology, type of systemic treatment, scan results, radiotherapy dose and schedule, further irradiation including re-irradiation. Patients will be followed till death but will only actively be followed for 9 weeks.

	Baseline	EOT	Daily Week 1-4 after start of RT	Daily Week 1-5 after start of RT	Weekly Week 1-5 after start of RT	Weekly Week 6-9 after start of RT
Signed consent	x					
Performance status	x					
Weight*	x	x			x	x
Registrations of analgesic, steroids, antacids and antidiabetic medication	x	x			x	x
EuroQol EQ-5D-5L Index*	x				x	x
EORTC QLQ-C30*	x				x	x
PRO Gastro-oesophageal symptoms*	x			x		x
PRO pain incl. numeric pain rating scale*	x			x		x
HbA _{1c}	x					
Flash glucose measurements			x			

Table 2 Schedule for visits and follow-up procedure. *Electronic questionnaire or telephone questionnaire

Quality of life

The QoL questionnaires EuroQol EQ-5D-5L Index and EORTC QoL C30, which are standardized and validated instruments, will be used to measure participants' quality of life (QoL) during follow up.

The EQ-5D index is a relatively simple five-item questionnaire (measuring mobility, self-care, usual activities, pain/discomfort, and anxiety/depression). It produces a composite score between 0 and 1 (multiplied by 100 to yield a result between 0-100).

The EORTC QoL C30 is more detailed and will be used to calculate measures for physical function.

See appendix B and D.

4.1 HbA_{1c} and Flash glucose monitoring.

HbA_{1c} will be measured at baseline. The blinded Flash glucose monitoring system FreeStyle Libre Pro (FreeStyle Libre Pro™; Abbott Diabetes Care, Witney, UK) will be used to obtain continuous glucose measurements for 28 days from baseline.^{19,20} The sensor must be changed after 14 days. This can be done in relation to another hospital appointment or by the patient at home with video assistance if necessary.

Data will only be extracted after the second sensor is dismantled. For quality assurance data will be extracted from the first sensor in the first 5 participants.

If the patients experience symptoms of hyperglycemia or hospitalized, glucose measurements will be at the discretion of the treating physician. See section 4.3 toxicity assessment.

4.2 Toxicity assessment

All toxicity assessment will be patient reported. If the patient cannot access the internet formula, the local investigator or a substitute will call them on the phone and record answers to the questions. QoL of Life schemes will be sent by mail. We will use the PRO symptom assessment that is found most suitable from an "pilot assessment" of different questions assessing oesophageal pain, difficulty swallowing, heart burn, nausea, pain from the irradiated volume and changes in pain medication. PRO symptoms will be daily assessed from start of radiotherapy and five weeks ahead,

from week 6-9 PRO symptoms will be assessed weekly. The participants will be reminded through a text message to their mobile phone or an email with a direct link to the eCRF in REDCap.

Patients participating in Flash glucose monitoring will be informed of symptoms of hyperglycaemia including needing to pee frequently, tiredness, recurrent infections and bad wound healing. See appendix E. Patients will be thoroughly instructed to contact the PI if symptoms of hyperglycaemia should occur. As many of the symptoms of hyperglycaemia overlap with symptoms related to end stage cancer, commencement of glucose measurements will be based on an individual assessment. If hospitalization is deemed necessary, glucose measurements will be at the discretion of the treating physician. If the patient is hospitalized for any reason, glucose measurements and treatment of hyperglycaemia if present, will be at the discretion of the treating physician.

The PRO questionnaire will contain a field where other symptoms not related to esophagitis can be recorded. See appendix A. If complete, this will appear as a pop-up message with the PI. Symptoms will then be assessed for symptoms of hyperglycaemia.

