The subjects will consent to participation in the study; regulatory authorities to gain full access to hospital records, to control the data collected in the study; recording, collecting and processing of data and storing data in a database. Contact information for the physician responsible of the study will be provided. If the subject chooses not to participate in the study, he or she will continue the standard treatment.

Patients may choose to participate in ESO-SPARE (esophagus sparing radiotherapy) or GLUC-DIAB (HbA_{1c} validation and glucose monitoring) only.

Participants will not be informed of randomization outcome.

Patients randomized to esophagus sparing radiotherapy needing reirradiation (**other target that primarily prescribed**) during the 9 weeks of FU, will receive esophagus sparing radiotherapy for the second target.

Participants will not receive remuneration.

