Unexpected:	If the treating physician/local investigator do not recognize the suspected SAE as an event reported in the literature and/or known from the clinical experience, this event should be considered as unexpected.

The assessment of an SAE should be based upon organs at risks that most likely will be affected from the radiation. Any suspected, unexpected SAE must be reported by the local investigator to the sponsor within one working day (after being aware of the incident). The sponsor can choose to change the registration of a suspected unexpected SAE to a suspected expected SAE after an audit of the case. The sponsor will inform the Ethical Committees of all relevant information about unexpected SAE, suspected to be related to the radiation treatment, that are fatal or life-threatening as soon as possible, and in any case no later than seven days after knowledge of such a case. Relevant follow-up information for these cases will subsequently be submitted within an additional eight days.

Once a year throughout the clinical trial, the sponsor will provide an updated safety report highlighting SAE to the Ethics Committee. For events not reported in the CTCAE version 5.0, the investigator will use the grade or adjectives reported in the following:

Grade 1 Mild does not interfere with patient's usual function

Grade 2 Moderate Interferes to some extent with patient's usual function

Grade 3 Severe, Interferes significantly with patient's usual function

Grade 4 Life-threatening, results in a threat to life or in an incapacitating disability

Grade 5 Death

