Data are reported by the patient in a paper-edition trial diary, by electronic questionnaires or by telephone consultations. Survival data, re-irradiation, and hospitalization data are derived from patient's treatment records. After the results of an interim analysis revealing low compliance (1), weekly CTC registrations were implemented for all patients in the first 5 weeks after treatment start (from patient No. 107).

Table 1. Follow-up schedule in the ESO-SPARE trial

	Treatment start	Daily	Weekly	Weekly
		1-5 weeks	1-5 weeks	1-9 weeks
PRO-CTC-AE: Dysphagia, nausea, dyspepsia	X	X		
CTC-AE 5.0*	X		X	
EORTC-QLQ-C30 and EQ-5D-5L	X			X
Medication: Analgesics, corticosteroids, antiemetics	X			
Weight	X			X

*Starting from patient No. 107

Estimated Enrollment: 200 patients.

Allocation: Patients are randomized 1:1 to either esophagus-sparring treatment or standard treatment. Patients are stratified by center and fractionation. Randomization is performed in REDCap using random allocation with a block size of four and six.

Masking: Single-blind. Patients are blinded to randomization outcome.

Study Start Date: May 2021

Estimated Primary Completion Date: April 2024

Study Completion Date: The last patient will be included on April 30, 2024, or after the inclusion of 200 patients, whichever comes first.

Timing of final analysis

Following study closure, nine weeks of follow-up after radiotherapy start will be allowed for all patients, at which point data will be collected for primary end-point analysis. Analysis of data in respect to secondary endpoints and exploratory studies might be analyzed at any point of time, at the discretion of the study group.

Data

Data are captured in REDCap. Data will be kept in databases 10 years after the last patient is included.

[Sample size](#)

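### Only patients are masked, yet the swallowing answers behind the dysphagia co-primary may be taken by telephone by a caller from whom nothing hides the arm

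*Protocol*

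**What the plan says.** **Masking.** The SAP (Trial design) states: "Masking: Single-blind. Patients are blinded to randomization outcome". Protocol 5.3 says the same: "Participants will not be informed of randomization outcome". No section of either document masks the investigator, the telephone caller, the person assigning CTC-AE grades or the analyst.

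**How answers are collected.** Protocol 4.2 makes telephone the fallback for patients who cannot reach the internet form: "the local investigator or a substitute will call them on the phone and record answers to the questions". The footnote to Protocol Table 2, which covers the gastro-oesophageal items, pain and EQ-5D-5L, reads "Electronic questionnaire or telephone questionnaire". Protocol 9.1 describes follow-up as electronic or by telephone, and Protocol section 4 also allows paper forms. The SAP lists three routes: "Data are reported by the patient in a paper-edition trial diary, by electronic questionnaires or by telephone consultations". Neither document gives the share by route.

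**What the answers feed.** The first item in Protocol Appendix A is severity of difficulty swallowing. Its peak over five weeks, scored 0 to 4 and compared by Wilcoxon rank-sum test, is the first co-primary in the SAP. The second is EQ-5D-5L mobility at nine weeks.

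**Added grading.** After an interim analysis showed low compliance, "weekly CTC registrations were implemented for all patients in the first 5 weeks after treatment start", starting with patient 107. The SAP lists these CTC-AE items, dysphagia among them, as secondary endpoints.

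**The concern.** Blinding the patient and using patient report is a sound way to protect a subjective endpoint when those who plan the radiotherapy must know the arm. It protects answers that patients enter themselves. When a caller reads the question and enters the reply, prompting and the coding of borderline answers (none or mild, for example) also depend on the caller. If the caller knows the arm, expectation could lower recorded dysphagia in the sparing arm. If mobility is collected the same way, expectation could mask a loss of walking ability.

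Two SAP rules make the primary score sensitive to this. The endpoint is a peak, so a single high answer recorded lower, or not obtained, can reduce a patient's score. Only weeks with at least three completed days count, so the effort put into calling can decide which weeks enter the analysis.

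As planned, nobody could show afterwards whether the telephone route affected the result, because no record of route and no analysis by route is foreseen.

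**Working it through.** **1. Could a caller know the arm?** Protocol 6.4 has a different planning aim in each arm. Protocol 5.3 and 6.4 require sparing again when a sparing-arm patient is treated for another target within nine weeks. Protocol 9.1 has re-irradiation watched by arm. The allocation is therefore known to some trial staff. That a given caller knows it is an inference from the absence of any masking beyond the patient; it is not stated.

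**2. The plan's own figure.** Inputs from Protocol 3.3: toxicity 0.6 against 0.3, alpha 0.05, power 0.9, Fisher's exact test. Full enumeration of the two-sided test gives power 0.902 at 61 and 0.910 at 62 per arm. The stated 62 per arm reproduces, and nothing in this point changes it.

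**3. How the effect would scale (purely illustrative).** The documents give neither a telephone share nor a misrecording rate, so both are assumed. Let *f* be the share collected by telephone and *m* the fraction of sparing-arm telephone patients with toxicity who are recorded as having none. With no true effect and 60% toxicity in both arms, the recorded sparing-arm rate is 0.6 × (1 − *f* × *m*). For example, *f* = 0.50 and *m* = 0.20 give 0.6 × (1 − 0.10) = 0.54. Chance that Fisher's test falsely favours sparing:

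| f | m | Recorded rate | 100 per arm | 62 per arm |
|---|---|---|---|---|
| 0 | – | 0.600 | 1.8% | 1.7% |
| 0.10 | 0.10 | 0.594 | 2.3% | 2.1% |
| 0.25 | 0.20 | 0.570 | 4.9% | 3.9% |
| 0.50 | 0.20 | 0.540 | 11.2% | 7.8% |
| 1 | 0.20 | 0.480 | 36.1% | 23.1% |

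The table shows only that the effect is negligible when telephone is rare and grows with its share. It uses the binary rate of the sample size section, whereas the SAP tests a 0–4 peak by Wilcoxon.

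**4. Mobility.** The Table 2 footnote permits EQ-5D-5L by telephone. Protocol 4.2 says quality-of-life forms are sent by mail. The two do not settle whether a caller records the mobility item.

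**5. CTC-AE grader.** Three passages bear on this and none decides it. Protocol 4.2 makes all toxicity assessment patient reported. Protocol 8.2 says that "the investigator will use the grade or adjectives reported in the following", but only for events outside CTCAE version 5.0. SAP analysis D scores the weekly items from none to very severe, the response words of the patient questionnaire. If numbering runs consecutively to 200, at most 200 − 106 = 94 patients have these grades.

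**The case against.** The strongest defence is that blinded patients choose among fixed answers, so a caller has little room to influence them. Telephone is a conditional route, paper is a further self-completed route, and the permitted substitute may well not know the arm. Protocol 8.2 names the local investigator and the treating physician separately, so the caller need not belong to the treating team. All of this stands. It is why the point is a risk and not a finding of bias.

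A reader might infer more in three places.

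- *A definite inflation of the false-positive rate.* The documents do not support one. Any figure needs an assumed telephone share. The any-to-none recoding also fits a peak poorly: a peak becomes none only if every symptomatic day is recorded as none, and in the pilot study described in Protocol 1.2 discomfort lasted 11 days on average. Lowering a peak by a grade is easier, but the table does not model that.
- *That unmasked staff grade CTC-AE.* The SAP names no grader, and the other passages point in different directions. These endpoints are also secondary, so they do not rank with the co-primary.
- *That mobility is collected in the same way as dysphagia.* The passages conflict, so this is not established.

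Timing is a fair objection too. Inclusion ends by 30 April 2024 or at 200 patients, and the SAP cites material accessed in March 2024. Changes to calling can reach only patients still in follow-up. A self-completed subset also probably leaves out frailer patients, so a difference from the main result could not be put down to the caller alone.

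**Conclusion.** The point holds as a risk of bias in the co-primary peak dysphagia score. Only patients are masked, a planned route lets an investigator record the answers, and nothing hides the arm from that person or tracks the route. The size is unknown: small if telephone was rare, material if it was common. The conclusion rests on the documents' silence about masking callers, not on evidence that any caller knew the arm or misrecorded an answer. Exposure of the mobility co-primary is possible but depends on reconciling Protocol Table 2 with 4.2. For CTC-AE, the defect is that the grader is not named. The sample size is unaffected. The changes are worth making because they are cheap, and the SAP part keeps its value even if follow-up is nearly complete.

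**What to change.** **Protocol 4.2, for patients still in follow-up.** Have telephone answers taken by an existing team member without access to allocation or dose plan; the substitute already provided for allows this. Require that items are read verbatim. Record the route (electronic, paper or telephone) for each entry, and reconstruct it for past entries where possible. Reconcile 4.2 with the Table 2 footnote on how EQ-5D-5L is collected.

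**SAP, before the arms are compared.** Report the telephone share by arm. Add a sensitivity analysis of both co-primary comparisons restricted to self-completed (electronic or paper) entries. State who assigned the weekly CTC-AE grades, and label those results unmasked where that is so.

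**Cost.** One route field, a short call script, restricted access to the allocation for callers, some reassigned calls and one extra analysis. Reconstructing past routes takes effort and may be incomplete. The self-completed subset is smaller and probably less frail, so its result is supportive only and should not replace the main analysis.
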